5.5 APPENDIX 5 SAMPLE SAS/R CODE

CMH analysis

The following SAS sample code would be used for the analysis:

```
proc freq data= ;
tables severity*treatment*response / cmh commonriskdiff(test=mh
CL>Newcombe) alpha=0.05;
ods output cmh commonPdiff CommonPdiffTests; /* CMH test for weighted
OR*/
run;
```

with severity as the PASI score at baseline (<=20 vs. >20).

MCP-mod analysis

The following R sample code would be used for the analysis:

```
require(DoseFinding)
##### Response #####
logit <- function(p){log(p / (1-p)) }
inv_logit <- function(y){1 / (1 + exp(-y) ) }
select.pbo.resp <- logit(0.13)
select.max.resp <- logit(0.54)-logit(0.13)
select.doses <- c(0, 50, 100, 200)

##### Candidate Curves #####
emax1 <- guesst(d = c(0,50, 100,200), p = c(0.13, 0.35, 0.4, 0.54),
model = "emax")
quad1 <- guesst(d = 150, p = 1, "quadratic")
quad2 <- guesst(d = 175, p = 1, "quadratic")
quad3 <- guesst(d = 100, p = 1, "quadratic")
my.model.list <- list(
  emax = c(20, emax1),
  logistic = c(50,15),
  linear = NULL ,
  exponential = max(select.doses) * 0.200,
  quadratic = quad1,
  placEff = select.pbo.resp,
  doses = select.doses ,
  maxEff = select.max.resp
```

```
)  
models.basic <- do.call( Mods , my.model.list)  
plotMods(models.basic)  
  
plotMods(models.basic, trafo = inv_logit)  
  
#Simulate the data for illustration purpose  
set.seed(1, kind = "Mersenne-Twister", sample.kind = "Rejection",  
normal.kind = "Inversion")  
group_size <- 24  
dose_vector <- rep(select.doses, each = group_size)  
N <- length(dose_vector)  
## generate covariates  
x1 <- rnorm(N, 0, 1)  
x2 <- factor(sample(c("A", "B"), N, replace = TRUE, prob = c(0.6,  
0.4)))  
## assume approximately logit(13%) placebo and logit(54%) asymptotic  
response with ED50=50  
prob <- inv_logit(emax(dose_vector, -1.9, 2.06, 50) + 0.3 * x1 + 0.3 *  
(x2 == "B"))  
dat <- data.frame(y = rbinom(N, 1, prob), dose = dose_vector, x1 = x1,  
x2 = x2)  
  
## fit logistic regression (without intercept), no covariates  
logfit <- glm(y~factor(dose)-1, family = binomial, data=dat)  
muHat <- coef(logfit)  
S <- vcov(logfit)  
  
MCTtest(select.doses, muHat, S=S, models = models.basic, type =  
"general")  
MCPMod(select.doses, muHat, S=S, models=models.basic, type = "general",  
Delta = 1.8)  
  
##fit logistic regression (without intercept), with covariates  
fit_cov <- glm(y~factor(dose) -1 + x1 + x2, data = dat, family =  
binomial)  
  
covariate_adjusted_estimates <- function(mu_hat, S_hat, formula_rhs,  
doses, other_covariates, n_sim) {  
  ## predict every patient under *every* dose  
  oc_rep <- as.data.frame(lapply(other_covariates, function(col)  
rep(col, times = length(doses))))  
  d_rep <- rep(doses, each = nrow(other_covariates))  
  pdat <- cbind(oc_rep, dose = d_rep)  
  X <- model.matrix(f  
rmula_rhs, pdat)  
  ## average on probability scale then backtransform to logit scale  
  mu_star <- logit(tapply(inv_logit(X %*% mu_hat), pdat$dose, mean))  
  ## estimate covariance matrix of mu_star
```

```
pred <- replicate(n_sim, logit(tapply(inv_logit(X %*%
drop(mvtnorm::rmvnorm(1, mu_hat, S_hat))), pdat$dose, mean)))
  return(list(mu_star = as.numeric(mu_star), S_star = cov(t(pred))))
}

ca <- covariate_adjusted_estimates(coef(fit_cov), vcov(fit_cov),
~factor(dose)+0+x1+x2, select.doses, dat[, c("x1", "x2")], 1000)

MCTtest(select.doses, ca$mu_star, S = ca$S_star, type = "general",
models = models.basic)
MCPMod(select.doses, ca$mu_star, S = ca$S_star, models=models.basic,
type = "general", Delta = 1.8)

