3.2.5 Exploratory analyses

[figure not shown]
Dose-response relationship

For NTIP population, the dose-response relationship of QD doses will be evaluated by a 2-step MCP-Mod procedure (2, 3) on the primary endpoint among three QD doses (200 mg QD, 100 mg QD and 50 mg QD) vs. placebo. The first step of this procedure tests for an efficacy signal (compared to the null hypothesis of a flat, no dose-response curve) in a procedure. To account for the uncertainty of the dose-response shape, [REDACTED]

[REDACTED] (see Figure 2 on logit scale and Figure 3 on original scale). The second step is the estimation of the dose-response curve, provided that an efficacy signal is established in the first step.

A logistic regression model with covariates for PASI75 response rate, treatment and baseline severity will be used to assess the response rate of PASI75 in each of 3 QD dose groups and placebo group at the end of 12 weeks treatment. A logit transformation of the PASI75 response rate will be entered into the MCP-Mod procedure (see R code in Appendix 5.5). The null hypothesis of a flat dose-response curve (ie, no dose-response relationship) at the end of 12 weeks treatment for the primary endpoint will be jointly evaluated for each of the 6 candidate dose response models with a contrast test at 2-sided alpha = 0.05. If step 1 yields significant results, the best fitting model (smallest AIC) from the 6 predefined candidate models will be chosen using the generalized AIC. The suggested optimal dose will then be estimated from the final selected model.

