4 SAMPLE SIZE DETERMINATION

A total sample size of approximately 207 participants will be randomized to the intervention groups in two different strata, ie, NTIP vs. ETIP.

In the stratum of NTIP, approximately 144 participants will be randomized in a randomization ratio 1:1:1:1:1:1 to SAR441566 200 mg BID, SAR441566 100 mg BID, SAR441566 200 mg QD, SAR441566 100 mg QD, SAR441566 50 mg QD and placebo, ie, 24 participants in each of six groups. The NTIP is the primary population for efficacy analysis.

In the stratum of ETIP, approximately 63 participants will be randomized in a randomization ratio 2:2:2:1 to SAR441566 200 mg BID, SAR441566 200 mg QD, SAR441566 100 mg QD and placebo, ie, 18 participants in each of SAR441566 200 mg BID, 200 mg QD and 100 mg QD groups and 9 participants in the placebo group. The ETIP is for exploratory purpose only.

In the NTIP, assuming a 10% dropout rate, the sample size of 24 participants per group will provide about █% power to demonstrate superiority of SAR441566 200 mg BID or 100 mg BID or 200 mg QD versus placebo with a 2-sided significance level of 0.05, based on Chi-square test with the following assumptions on the primary endpoint:

- PASI75 Placebo rate of █%.
- PASI75 SAR441566 rate of █%.

To estimate the dose-response curve on QD regimen in the NTIP, the sample size of 24 participants per group will provide an minimum power of █% to detect the presence of a dose response, based on the assumption of a maximum effect in terms of PASI75 of treatment difference of █% in SAR441566 comparing with placebo rate of █%, using █
█
█.

Calculations for Chi-square test were done using █
█

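### The exploratory QD dose-response test is stated at 2-sided 0.05, but near the SAP's 13% planning rate its Wald-logit contrasts run at about 1.4–2.3%, which costs power

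*SAP*

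**What the plan says.** SAP 3.2.5 (Dose-response relationship) applies a two-step MCP-Mod procedure to Week 12 PASI75 in the NTIP, using placebo and 50, 100 and 200 mg QD. In step 1 the flat-curve null is "jointly evaluated for each of the 6 candidate dose response models with a contrast test at 2-sided alpha = 0.05". The inputs are logits from a logistic regression on treatment and baseline severity. Step 2 (model choice by AIC, curve estimate, suggested optimal dose) follows only if step 1 is significant.

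The sample R code in SAP 5.5 fits dose as a factor by maximum likelihood and averages the predicted probabilities over covariates. It returns to the logit scale, builds a covariance matrix from simulated draws, and calls "MCTtest(select.doses, ca$mu_star, S = ca$S_star, type = 'general" with the candidate models. The call sets no significance level, alternative, degrees of freedom or critical value. The doses are "select.doses <- c(0, 50, 100, 200" and the placebo rate is "select.pbo.resp <- logit(0.13". SAP section 4 plans 24 per group.

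No permutation, exact or other small-sample calibration is visible. Part of 3.2.5 and the planned MCP-Mod power are blacked out.

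**The concern.** At 13%, a group of 24 expects 0.13 × 24 = 3.1 responders. With counts that small, a Wald statistic on the logit scale is conservative. When a group falls well below the others its logit moves far, but its estimated variance, 1/y + 1/(24 − y), grows faster. The statistic shrinks just when the evidence is strongest, so a normal critical value is exceeded too rarely.

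The stake is limited but real. Step 1 decides whether the QD curve and the suggested optimal dose are estimated at all, and protocol 4.1 names the choice of dose regimen as an objective. A missed signal at step 1 leaves the planned modelling step undone.

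**Working it through.** **Inputs.**
- Two-sided 0.05 and "6 candidate dose response models" (SAP 3.2.5).
- Four equal groups of 24 (SAP 4). Missing responses count as non-response (SAP 3.2.2), so n stays at 24.
- Placebo rate 13%, maximum 54%, target 47.5% (SAP 5.5).
- Shapes from SAP 5.5: Emax with ED50 20; Emax from the listed rates; logistic (50, 15); linear; exponential (0.2 × 200 = 40); quadratic with peak at 150.
- The second Emax ED50, read as the mean of d(1 − p)/p over the four listed points, is (0 + 92.9 + 150.0 + 170.4)/4 = 103.3.

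**The plan's own figures.** The threshold Delta reproduces: ln(0.475/0.525) − ln(0.13/0.87) = −0.100 + 1.901 = 1.801, against 1.8 in the code. The 5% level does not reproduce (below). The planned power is blacked out and cannot be checked.

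**Mechanism in one pair.** Take 1/24 vs 6/24 responders, pooled rate 7/48 = 14.6%.
- Wald logit: difference ln(6/18) − ln(1/23) = 2.037; variance 1/6 + 1/18 + 1/1 + 1/23 = 1.266; z = 2.037/1.125 = 1.81.
- Score: difference 5/24 = 0.208; variance 0.1458 × 0.8542 × 2/24 = 0.01038; z = 0.208/0.1019 = 2.04.

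Neither group is empty, yet the Wald statistic is clearly the smaller.

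**Simulation of step 1.** With estimated logits m and covariance S, shape j has contrast c_j ∝ S⁻¹(μ_j − μ̄_j·1), where μ̄_j = 1′S⁻¹μ_j / 1′S⁻¹1, and T_j = c_j′m / √(c_j′Sc_j). The test rejects if max|T_j| exceeds the multivariate-normal 5% critical value. Unadjusted, 30,000–60,000 trials per point (Monte Carlo SE about 0.05–0.12 points):

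| Flat PASI75 rate | 10% | 13% | 15% | 18% | 20% | 30% | 40% | 54% |
|---|---|---|---|---|---|---|---|---|
| Real 2-sided level | 1.1% | 1.5% | 1.9% | 2.3% | 2.6% | 3.3% | 4.1% | 4.2% |

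Other simulations at 13% gave 1.4–1.9% unadjusted. Severity-adjusted versions gave 1.5%, 1.7% (with the code's 1,000-draw covariance, groups without responders counted as non-rejections) and 1.9–2.3% (with a delta-method covariance, which is not the code's).

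**Comparators with the same shapes.** A permuted score max-contrast test has level 4.9% at 13% and 4.7–5.0% from 10% to 54%, falling to 3.5% at 5%. Score versions with asymptotic critical values gave 4.3–5.1%. The six-model adjustment and the discreteness of the data are therefore not the main cause.

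**Groups without responders.** At 13% one group is empty with probability 0.87²⁴ = 0.035, and at least one of four with probability 1 − (1 − 0.035)⁴ = 13%. Among trials with no empty group the level is still 1.2–1.6% at 13%, so this is not only an empty-group effect.

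**Power, unadjusted, 2-sided (%).** Gains are from unrounded values where available. The two halves come from separate simulations. In the 47.5% half, 0.5 was added only where a group was empty or full.

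| Shape | 47.5% vs 13%: Wald | Score | Gain | 54% vs 13%: Wald | Permutation | Gain |
|---|---|---|---|---|---|---|
| Emax 20 | 67.9 | 77.2 | 9.3 | 82.6 | 90.3 | 7.8 |
| Emax 103 | 68.9 | 75.6 | 6.7 | 84.0 | 88.2 | 4.2 |
| Logistic | 79.5 | 83.8 | 4.3 | 90.0 | 93.1 | 3.2 |
| Linear | 72.7 | 77.9 | 5.2 | 85.8 | 89.9 | 4.0 |
| Exponential | 82.3 | 87.7 | 5.4 | 92.8 | 95.4 | 2.6 |
| Quadratic | 77.6 | 84.0 | 6.4 | 89.0 | 93.2 | 4.2 |

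In unadjusted trials with no empty group the gains are about 3–7 points at 47.5% and 1–3 points at 54%.

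**The case against.** **The stakes are low.** The analysis is headed exploratory, SAP 3.5 treats p-values outside the primary hierarchy as nominal, and alpha is an upper bound that a conservative test respects. All of this stands. A reader might infer that error control fails or that a confirmatory conclusion is at risk; the documents support neither.

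**The level depends on the flat rate.** A reader might take 1.4–2.3% as a property of 24 per group. It is not: at 40% or more the level is about 4%.

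**Other dose information survives.** A reader might infer that step 1 gates all dose-response evidence. SAP 3.2.2 gives every one of the five doses a difference from placebo with a 95% CI, and protocol 8.5 allows exposure-response modelling. Only the QD curve fit is gated.

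**The power loss is not one number.** A severity-adjusted run, assuming 40% with PASI >20 and a severity odds ratio of 0.7 (neither is in the documents), with a delta-method covariance, gave smaller gains from a stratified score test: 0.8–5.9 points at 47.5% and 0.2–2.8 at 54%. Another, with the code's simulated covariance and empty groups counted as failures, gave about 4–9 at 54%. Part of the gain in some runs belongs to empty-group handling. The objection stands against any single figure, but not against the direction.

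**Redaction.** The planned power may have been simulated with this same test, so the conservatism may already be in the sample size. No claim that the trial is underpowered can be made.

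**The code is a sample.** True, but 3.2.5 prescribes logits from a logistic model and gives no other calibration. If the call were run one-sided at 0.025 (an assumption about software defaults), the level at 13% would be 0.8%, also well below nominal.

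**Conclusion.** The point holds for flat PASI75 rates near the planning value. At 13% the step-1 test has a real two-sided level of about 1.4–2.3% instead of 5%; at 20% it is about 2–3%. The consequence is a higher chance of missing a QD dose response: roughly 3–9 points of power at 47.5% vs 13% and roughly 1–8 points at 54% vs 13%, with some runs just outside those ranges. The pairwise comparisons with placebo are unaffected.

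This assumes 24 analyzed per group, the six shapes as coded, multivariate-normal critical values (the call supplies a covariance and no degrees of freedom) and the two-sided 0.05 of the text. It merits a change because the remedy is cheap, not because any planned conclusion would be wrong.

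**What to change.** In SAP 3.2.5 and 5.5, keep the six candidate shapes and obtain the step-1 p-value in one of two ways:

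- a permutation distribution of the maximum contrast, shuffling responses across placebo and the three QD groups within baseline PASI ≤20 and >20, with a fixed seed and a stated rule for groups with no responders, applied alike to observed and permuted data; or
- severity-stratified score contrasts with the candidate shapes as dose scores, which matches the stratified CMH test used for the primary endpoint.

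The choice of statistic matters. In the severity-adjusted simulation, permuting the planned Wald statistic gained about 2–3.5 points at 47.5% vs 13%. The larger gains in the table used score statistics.

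State two-sided 0.05 in the code as well as the text, and leave the modelling step unchanged. The cost is SAP wording, short extra code, some computing time and departure from the package's default p-value. No new data are needed.

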##### The clinical relevance threshold Delta=1.8 given by logit(0.475)-
logit(0.13) for the target effect of 47.5% vs. 13%.
```

ANCOVA analysis

The following SAS sample code would be used for the analysis:

```
proc mixed data=;
class treatment (ref='Placebo');
model percentChange = base treatment / outp=predicts residual;
estimate 'SAR441566 50 mg QD' treatment 1 0 0 0 0 -1 / e alpha=0.05;
estimate 'SAR441566 100 mg QD' treatment 0 1 0 0 0 -1 / e alpha=0.05;
estimate 'SAR441566 200 mg QD' treatment 0 0 1 0 0 -1 / e alpha=0.05;
estimate 'SAR441566 100 mg BID' treatment 0 0 0 1 0 -1 / e alpha=0.05;
estimate 'SAR441566 200 mg BID' treatment 0 0 0 0 1 -1 / e alpha=0.05;
lsmeans treatment / diff=control('Placebo') cl e alpha=0.05;
ods output diffs lsmeans;
run;
```

Time-to-event analysis

The following SAS sample code would be used for the Kaplan-Meier analysis:

```
proc lifetest data= method=km alphaqt=0.05;
id usubjid;
time 'time period' * EVENT(1);
strata treatment;
run;
```

with 'time period' as the number of months between first IMP and date of event or censoring.

The following SAS sample code would be used for the Cox Proportional Hazard Model analysis:

```
proc phreg data=;
class treatment (ref='placebo') / param=ref;
model 'time period' * EVENT(1) = treatment / risklimits alpha=0.05;
strata severity;
```

run;

with 'time period' as the number of months between first IMP and date of event or censoring and 'severity' as the PASI score at baseline (<=20 vs. >20).

5.6 APPENDIX 6 IMPUTATION RULES FOR START DATES OF MEDICATION IN ICE

The date format is: YYYY-MM-DD

1. If the year is missing
 - No imputation can be done. Medication will be assumed to start prior to the randomization date. Set the date to one day before the randomization date.
2. If the month is missing and year is not missing
 - If year is equal to year of randomization date, then set the date of one day prior the randomization date
 - If year is not equal to year of randomization date, then Impute day and month with 01-January
3. If the day is missing and year and month are not missing:
 - Impute the day with 01
 - Exception: If the given year and month (YYYY-MM) correspond to the randomization date's year and month, impute one day before the randomization date.
 - Example:
 - If the IE start date is 2024-03, the imputed date is 2024-03-01.
 - However, if the randomization date is 2024-03-08, the imputed date will be 2024-03-07.

